7.1.14. Change in PA pressure

Change from baseline in PAP parameters collected via CorPASS: pulmonary artery pressure systolic, pulmonary artery pressure diastolic, pulmonary artery pressure mean and pulse will be presented by treatment group by means of descriptive statistics at before and after 6-minute walk test.

mPAP will be summarized by 'Above target range', 'Within or below target range', and 'Overall' for subjects with a baseline mPAP, at all study visits as described in [Appendix 1: Time and Event Schedule](#) including post implant measurement, and sitting vs. supine measurements. Shifts in mPAP from baseline over all post-baseline visits will be presented. Target range of mPAP is 5-20 mmHg. When there are more than one available results collected on same visit, please use the earliest one.

Analysis will be done based on mITT population, and PP population. Prior to the date of cut-off for the main analysis, it will be confirmed, if analysis based on PP population will be required.

This document is confidential.

7.1.15. Percentage of device success as documented by ability of the System to successfully transmit PAP data

For the analysis of this endpoint, external data, provided by Endotronix, will be used. The provided data will include information if the missing PAP data are due to the System issues.

Following derived parameters will be presented:

- A) Total overall number of days of data collection, defined as the sum of all planned collection days (until end of study for final analysis or date of early discontinuation or date of cut-off or date of V6, Month 12 for the main analysis, whichever is smaller) of all subjects, excluding the days with missing data collection due to the subject's missing data transmission.
- B) Number of days with missing overall successful transmission of the collected data due to the System issues, defined as the sum of all unavailable days due to the System issues (until end of study for final analysis or date of early discontinuation or date of cut-off or date of V6, Month 12 date for the main analysis, whichever is smaller) of all subjects
- Overall device success rate of transmission (%), defined as $A-B/A * 100$
- Per subject device success rate will be calculated similar to the rules above, based on per subject data only.

Per subject device success rate will be presented by means of descriptive statistics, overall device success rate as percentage, other parameters will be presented using counts.

Presentation will be done overall as all parameters are transmitted together.

Analysis will be done based on mITT population, PP population, and Cohort #1 population. Prior to the date of cut-off for the main analysis, it will be confirmed, if analysis based on PP population will be required.

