3.3 Clinical Studies of the Cordella PA Sensor System

In the US, no prior clinical studies have been performed to evaluate the Cordella™ Heart Failure system with the Cordella PA Sensor System.

In Europe, Endotronix has currently two studies ongoing: 1. SIRONA (NCT03375710), a First in Human (FIH) study and 2. SIRONA 2 (NCT04012944) study, our CE mark study.

1. SIRONA 1: The FIH study is ongoing at 2 centers in Europe. Overall, 15 patients have been implanted. The primary safety endpoint is freedom from adverse events associated with the use of the Cordella™ Heart Failure System through 30 days post index procedure. The primary efficacy endpoint is measurement of the correlation of Cordella PA Sensor pressure measurements compared with pressure measurements (Swan Ganz) obtained by standard RHC at 90-day post index procedure. In this FIH study, the patients use the Cordella PA Sensor System in combination with the Cordella™ HF System. All patients were successfully implanted with the Cordella PA Sensor without device system related complication or sensor failure. The primary efficacy endpoint of a mean PAP was met in all patients with a cohort difference of 2.7 mmHg (Cordella PA Sensor 22.5 mmHg +/-11.8, Swan-Ganz 25.2 mmHg +/-8.5). Patient adherence to daily measurement and transmission of vital signs was 99% and Cordella PA Sensor readings compliance was 99%⁴⁵. This study is ongoing and in long- term follow up, to date no safety or efficacy concerns have been reported.

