10.2.5 Cohort #1- Previously enrolled Control Arm subjects- Population

This subgroup will include all Cohort #1 (previously enrolled Control Arm) subjects and will be reported separately for all endpoints.

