2.1	17-Aug-2023	[name]	
Repeated the primary safety analysis on ITT additionally. The cutoff for 6 month analysis updated to 180 days from 183 days
 
Added an AE summary for 'Other serious adverse events (AE) CEC adjudicated'
 
Added separate analyses of HFH and all-cause mortality from CEC adjudication results
 
The compression population update to Cohort #1, Cohort #2 and #3 from Cohort #1 and Cohort #2
 
The secondary endpoint #3 update to Comparison of the number of HF Hospitalizations or Emergency Department/ Hospital Outpatient IV diuretic visits of Cohort #1 and Cohort #2 + #3 at 6 and 12 months post implant from Comparison of the number of HF Hospitalizations or Emergency Department/ Hospital Outpatient IV diuretic visits of Cohort #1 and Cohort #2 at 6 and 12 months post implant
 
The secondary endpoint #14 Change from baseline in PAP parameters collected via CorPASS will not be performed for Cohort #1 population

This document is confidential.

I confirm that I have reviewed this document and agree with the content.

Approvals		
Syneos Health Approval		
[name], Biostatistician I	[name]	<small>Electronically signed by: [name] Reason: I am the author Date: Aug 17, 2023 14:58 GMT+8</small>
Lead Biostatistician	Signature	Date (DD-Mmm-YYYY)
[name], Principal Stat Programmer	[name]	<small>Electronically signed by: [name] Reason: I am the approver Date: Aug 17, 2023 10:28 GMT+2</small>
Lead Statistical Programmer	Signature	Date (DD-Mmm-YYYY)
[name], Assoc Dir, Biostatistics	[name]	<small>Electronically signed by: [name] Reason: I am the reviewer Date: Aug 17, 2023 17:52 GMT+8</small>
Senior Reviewing Biostatistician	Signature	Date (DD-Mmm-YYYY)
Endotronix, Inc.		
[name], Vice President Clinical Operations	[name]	<small>Electronically signed by: [name] Reason: I am the approver Date: Aug 17, 2023 09:11 GMT+2</small>
Sponsor Contact	Signature	Date (DD-Mmm-YYYY)

This document is confidential.

Table of Contents

Revision History	2
Approvals	3
1. Purpose.....	11
1.1. Responsibilities	11
1.2. Timings of Analyses.....	11
2. Study Objectives.....	12
2.1. Study Objective	12
2.2. Brief Description	12
2.3. Subject Selection.....	15
2.3.1. Inclusion Criteria.....	15
2.3.2. Exclusion Criteria.....	15
2.4. Determination of Sample Size.....	16
2.4.1. Primary Efficacy Endpoint (at 6 months post- implant).....	16

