5.1. General Methods

- Unless otherwise specified, summaries will be presented by cohort (cohort #2 vs cohort #3) and overall
- Continuous variables will be summarized using the number of observations (n), mean, standard deviation (SD), median, minimum, and maximum. Categorical variables will be summarized using number of observations (n), frequency and percentages of subjects.
- All relevant subject data will be included in listings. All subjects entered into the database will be included in subject data listings, except screen failures. A separate listing will present the screen failures along with the inclusion criteria they failed and/or exclusion criteria they met. All listings except 16.2.3.x will be repeated for Cohort #1 population.
- In case of multiple assessments at a given time point (planned, repeat, unscheduled) the planned visit will be used for the analysis. For the definition of the baseline value, the last available value (e.g. unscheduled) prior to implant of Cordella PA Sensor will be used.

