6.5.2. Concomitant Medication

Medications taken at/after the date of implant will be summarized as 'Concomitant' medications.

This document is confidential.

7. Efficacy

The population used for efficacy analyses will be the mITT. In addition, all efficacy analysis will be analyzed based on PP population and Cohort #1 population. For CEC related endpoints, tables and figures will be repeated using CEC adjudication results

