Header	Table Number	Name	Analysis Set
	16.2.4.5.1	Baseline and concomitant medications	Cohort #1 Population
16.2.5		System Use Compliance – Not applicable	
16.2.6		Individual Efficacy Data	
	16.2.6.1	Cordella sensor implant	Enrolled Population
	16.2.6.2	Mortality	Enrolled Population
	16.2.6.2.1	Mortality	Cohort #1 Population
	16.2.6.3	Hospitalization	Enrolled Population
	16.2.6.3.1	Hospitalization	Cohort #1 Population
	16.2.6.4	Emergency department/hospital outpatient IV diuretic visits	Enrolled Population
	16.2.6.4.1	Emergency department/hospital outpatient IV diuretic visits	Cohort #1 Population
	16.2.6.5	Heart failure related medication changes	Enrolled Population
	16.2.6.5.1	Heart failure related medication changes	Cohort #1 Population
	16.2.6.6	Cordella sensor PAP measurements	Enrolled Population
	16.2.6.7	Quality of life KCCQ questionnaire	Enrolled Population
	16.2.6.7.1	Quality of life KCCQ questionnaire	Cohort #1 Population
	16.2.6.8	NYHA functional classification	Enrolled Population
	16.2.6.8.1	NYHA functional classification	Cohort #1 Population
	16.2.6.9	Six (6) minute walk test	Enrolled Population
	16.2.6.9.1	Six (6) minute walk test	Cohort #1 Population
	16.2.6.10	RHC PAP measurements	Enrolled Population
	16.2.6.10.1	RHC PAP measurements	Cohort #1 Population
16.2.7		Adverse Event Listings	
	16.2.7.1	Adverse events	Enrolled Population
	16.2.7.1.1	Adverse events	Cohort #1 Population
	16.2.7.2	Device/system related complications	Enrolled Population
	16.2.7.2.1	Device/system related complications	Cohort #1 Population
	16.2.7.3	Device Deficiency	Enrolled Population
	16.2.7.3.1	Device Deficiency	Cohort #1 Population
	16.2.7.4	Predefined adverse events by category adjudicated by CEC	Enrolled Population
	16.2.7.4.1	Predefined adverse events by category adjudicated by CEC	Cohort #1 Population
	16.2.7.5	CEC adjudication results	Enrolled Population
	16.2.7.5.1	CEC adjudication results	Cohort #1 Population

This document is confidential.

Header	Table Number	Name	Analysis Set
16.2.8		Listing of individual laboratory measurements by subject	
	16.2.8.1	Clinical Laboratory Data	
	16.2.8.1.1	Hematology	Enrolled Population
	16.2.8.1.1.1	Hematology	Cohort #1 Population
	16.2.8.1.2	Chemistry	Enrolled Population
	16.2.8.1.2.1	Chemistry	Cohort #1 Population
	16.2.8.1.3	Urinalysis	Enrolled Population
	16.2.8.1.3.1	Urinalysis	Cohort #1 Population
	16.2.8.1.4	Coagulation	Enrolled Population
	16.2.8.1.4.1	Coagulation	Cohort #1 Population

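### SAP 7.1.14 leaves Cohort #1 out of the change-in-PAP endpoint, against the protocol and the SAP's own general rules and without a stated reason, so the endpoint loses its only comparator of randomised origin at Months 6 and 12

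*SAP*

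**What the plan says.** SAP 7.1.14 plans descriptive statistics and shift tables for sensor PAP, by baseline mean PAP (mPAP) stratum and overall. It then limits the populations: "Analysis will be done based on mITT population, and PP population". Both sets contain only Cohorts #2 and #3.

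The SAP revision history for version 2.1 confirms that this is intended: "The secondary endpoint #14 Change from baseline in PAP parameters collected via CorPASS will not be performed for Cohort #1 population". It numbers the endpoint 14, but PAP change is endpoint 11 in SAP 3.3; 7.1.14 is the section number.

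Three general statements point the other way:

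- Protocol 10.2.5: Cohort #1 "will be reported separately for all endpoints".
- Opening of SAP section 7: "In addition, all efficacy analysis will be analyzed based on PP population and Cohort #1 population".
- SAP 5.1: "All listings except 16.2.3.x will be repeated for Cohort #1 population".

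The output indexes follow the exclusion. Tables 14.2.2.11.1 to 14.2.2.11.8 cover mITT and Per Protocol only. Listing 16.2.6.6, "Cordella sensor PAP measurements", is for the Enrolled Population only, while right heart catheter (RHC) PAP is listed for Cohort #1 (16.2.6.10.1).

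**The concern.** PAP is the variable that the guided therapy acts on, so its change is the natural check that the intervention did what it was meant to do. Without Cohort #1, endpoint 11a is a before/after change with no comparator. Such a change mixes guided care with several other things:

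- background therapy and the natural course of the disease;
- regression to the mean, chiefly in the stratum with baseline mPAP above target;
- a change of measurement route. Baseline is the pre-discharge reading at the implant visit (SAP 5.2), taken through the calibration equipment; follow-up readings come through the patient app and may be taken at home (Protocol 8.1.18 and 14.1);
- possibly, a sensor offset after calibration.

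Cohort #1 had the same implant, and its sensor PAP follows the same visit schedule. Its clinicians started managing to PAP only after unblinding (Protocol section 6). Its readings before that date, set against Cohort #2, are the only comparison of randomised origin at Months 6 and 12, and influences shared by the two cohorts would largely cancel in the difference. The SAP already uses Cohort #1 as a comparator for endpoint 3 (SAP 4.6 and 7.1.6), but not for PAP.

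**Working it through.** **1. Is the exclusion explained anywhere?** The neighbouring secondary endpoints (SAP 7.1.12, 7.1.13, 7.1.15, 7.1.16 and 7.1.17) all name Cohort #1; 7.1.14 does not. The version 2.1 history states the decision without a reason. SAP section 10, which lists changes from the protocol, has three items, and this is not one of them. Protocol 10.1 requires departures from the planned analyses to be reported with justification. SAP 7.1.14 also still refers to presentation by treatment group, a trace of the two-arm design.

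**2. How long is Cohort #1 usable as a comparator?** Blinding ends at Visit 6 (Month 12) or at cross-over, whichever comes first (Protocol 14.1, note 13). The contrast is one of clinician blinding, because subjects in Cohorts #2 and #3 also do not see their own PAP before Month 12 under the design text.

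Inputs: up to 85 subjects in Cohort #1 (Protocol 6.1); first implant in the fourth quarter of 2019 (Protocol 6.3); redesign dated 11 November 2021 (amendment history), about 24 months later. Assuming even accrual over 24 months:

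- six blinded months: 85 × (24 − 6)/24 = 63.75, about 64 subjects;
- twelve blinded months: 85 × (24 − 12)/24 = 42.5, about 42 subjects.

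If the period is taken as 18 to 27 months, the ranges are 57 to 66 and 28 to 47 subjects.

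**3. How precise would the contrast be?** The plan gives no SD for mPAP change and no size for Cohort #2, so there is no planned figure to reproduce. Assumed: SD 6 to 8 mmHg and 85 subjects in Cohort #2.

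Half-width of the 95% CI = 1.96 × SD × √(1/n₁ + 1/85), with n₁ the number in Cohort #1 still blinded.

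| Visit | n₁ | SD (mmHg) | Half-width (mmHg) |
|---|---|---|---|
| Month 6 | 85 | 6 | 1.80 |
| Month 6 | 64 | 7 | 2.27 |
| Month 6 | 64 | 8 | 2.60 |
| Month 6 | 64 | 10 | 3.24 |
| Month 12 | 42 | 6 | 2.22 |
| Month 12 | 42 | 8 | 2.96 |

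The SD 10 row shows sensitivity outside the assumed range.

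**4. Can the documents size a sensor offset?** Protocol 3.3 reports for SIRONA 1 (15 implanted) a "cohort difference of 2.7 mmHg (Cordella PA Sensor 22.5 mmHg +/-11.8, Swan-Ganz 25.2 mmHg +/-8.5" at 90 days, with no interval. If all 15 were paired and the within-pair correlation were 0.9:

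- SD of the difference = √(11.8² + 8.5² − 2 × 0.9 × 11.8 × 8.5) = √30.95 = 5.56 mmHg;
- half-width = 2.145 × 5.56/√15 = 3.1 mmHg, so the interval around 2.7 includes zero. It excludes zero only if the correlation is above about 0.94.

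SIRONA 2 gives 0.0 to 2.9 mmHg without stating the direction, and met its ±4.0 mmHg equivalence bounds. Neither study says whether any offset arose after implant calibration. An offset is possible, but its size is not established.

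**The case against.** The exclusion is a recorded decision that agrees with the current text of 7.1.14, not an oversight. SAP 4.5 limits Cohort #1 reporting to outputs that are applicable, and the index does not follow SAP 5.1 to the letter elsewhere: listing 16.2.6.1 has no Cohort #1 version either. The PAP endpoint is descriptive, and Protocol 10.4 makes its p-values and intervals nominal. The lack of a control stems from the single-arm redesign. Protocol 10.2.5 promises separate reporting; a between-cohort difference goes beyond that.

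Most of this stands, and it limits the point. It does not supply a reason for dropping this one endpoint, and it does not reconcile 7.1.14 with Protocol 10.2.5.

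A reader might also infer more than the documents support:

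- That Cohort #1 is the only control for sensor drift. RHC at Year 3 and for recalibration (Protocol 8.1.17) also bears on drift, although none is scheduled at Month 6 or 12.
- That the Cohort #1 PAP data are discarded. Nothing stops their collection; they are not tabulated or listed.
- That up to 3 mmHg of any fall is drift. That would rest on 15 patients without an interval and on a SIRONA 2 interval of unknown direction.
- That the plan wrongly attributes a PAP fall to guided care. No such attribution is pre-specified and no result is known.

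**Conclusion.** The point holds as an unexplained conflict between documents with an analytic cost. SAP 7.1.14, its tables and listing 16.2.6.6 depart from Protocol 10.2.5, the opening of SAP 7 and SAP 5.1. The departure is deliberate, but it is unjustified and missing from SAP section 10. The cost is that endpoint 11a stays uncontrolled although a partial remedy is available from readings already scheduled.

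The remedy is modest. Precision of about 1.8 to 2.6 mmHg at Month 6 rests wholly on assumed SDs (6 to 8 mmHg), an assumed 85 subjects in Cohort #2, and 64 to 85 Cohort #1 subjects still blinded. At Month 12, with about 42 still blinded, it is about 2.2 to 3.0 mmHg. That is adequate for an exploratory estimate, not for a firm claim. The change should be made; it does not affect the primary analysis.

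**What to change.** In SAP 7.1.14:

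- Add the Cohort #1 population to the text, to tables 14.2.2.11.x and to listing 16.2.6.6, with readings split at each subject's unblinding date.
- Add an exploratory, baseline-adjusted Cohort #2 minus Cohort #1 difference in mPAP change at Month 6, and at Month 12 for Cohort #1 subjects still blinded, with a nominal 95% CI. Leave Cohort #3 out of this contrast, as it was never randomised.
- Present the uncontrolled Cohort #2 and #3 change beside it, and mention sensor offset only as a possibility.

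Withdraw the version 2.1 exclusion, refer to the endpoint as number 11, and list the added contrast in SAP section 10. If the sponsor keeps the exclusion, section 10 should give the reason, and the general statements in SAP 5.1 and 7 should be amended to match.

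The cost is SAP wording and a few tables, with no new measurements. The downside is a small comparator: at most 85 subjects, with fewer still blinded at Month 12.

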7.1.16. Subject Outcome Measures, measured by Quality of Life KCCQ questionnaire

The Quality of Life KCCQ questionnaire is a measure of health-related quality of life. Data will be collected at the study visits described in [Appendix 1: Time and Event Schedule](#). For the analysis of this endpoint, external data, provided by Endotronix, will be used.

The KCCQ is a 23-item, refer to Protocol, section 14.4, self-administered instrument that quantifies physical function, symptoms (frequency, severity, and recent change), social function, self-efficacy and knowledge, and quality of life related to HF.

Out of 23-items, 10 scores will be calculated according to the rules in [Appendix 2: The Kansas City Cardiomyopathy Questionnaire Scoring Instructions](#): Physical Limitation, Symptom Stability, Symptom Frequency, Symptom Burden, Total Symptom Score, Self-Efficacy, Quality of Life, Social Limitation, Overall Summary Score, Clinical Summary Score.

Presentation will be done by means of descriptive statistics including the absolute value and change from baseline by visit.

Analysis will be done based on mITT population, PP population, and Cohort #1 population. Prior to the date of cut-off for the main analysis, it will be confirmed, if analysis based on PP population will be required.

7.1.17. Functional status improvement measured by NYHA and 6-Minute Walk Test

NYHA functional classification: The subject's functional status is assessed by a qualified individual at the institution, who is not directly involved with this clinical trial, by utilizing the NYHA functional classification, described in the Protocol Appendix 14.2.

The NYHA functional classification categorizes the extent of heart failure by placing subjects in one of four (I, II, III, IV) categories based on how much they are limited during physical activity and symptoms of shortness of breath and/or angina.

This document is confidential.

NYHA functional classification will be obtained at all study visits as described in [Appendix 1: Time and Event Schedule](#) and must be NYHA Class III for study entry.

Shifts in NYHA functional classification from baseline over all post-baseline visits will be presented.

Six (6) Minute Walk: Subjects complete a six (6) minute walk test at the study visits described in [Appendix 1: Time and Event Schedule](#). Total distance walked (meters) will be collected and analyzed by means of descriptive statistics including the absolute value and change from baseline by visit.

Analysis will be done based on mITT population, PP population, and Cohort #1 population. Prior to the date of cut-off for the main analysis, it will be confirmed, if analysis based on PP population will be required.

This document is confidential.

8. Safety

The population used for safety analyses will be the ITT. Safety will be assessed on the basis of adverse events (AEs), clinical laboratory data, ECG parameters, Echocardiograms, physical examinations, and vital signs. Primary safety endpoint will be analyzed based on mITT. In addition, AEs will be analyzed based on Cohort #1 population. Primary safety endpoints will also be repeated on ITT, PP population and Cohort #1 population. Secondary safety endpoints will also be analyzed based on PP population and Cohort #1 population. For CEC related endpoints, tables and figures will be repeated using CEC adjudication results

Adverse events and other safety analyses will also be assessed. No formal statistical hypothesis tests will be conducted. Analyses will involve Kaplan-Meier curves for time to event outcomes, descriptive statistics (n, mean, standard deviation, median, minimum, and maximum) for quantitative outcomes, and count and frequency results for categorical outcomes.

Safety analysis will be performed in first line to address the safety endpoints:

8.1. Primary safety endpoint

8.1.1. Main analysis

There are two primary safety endpoints:

- 1) Freedom from device/system related complication at 6 months. Freedom from device or system related complications at 6 months will be tested against the null rate of 90%. The endpoint will be assessed based on the AE CRF page with adverse event type = 'Device / System-Related Complication'
- 2) Freedom from pressure sensor failure at 6 months. Freedom from Pressure Sensor Failure at 6 months will be tested against the null rate of 95%. The endpoint will be assessed based on the AE CRF page with adverse event type = 'Pressure Sensor Failure'

Each of these will be assessed within among all subjects who underwent a device implant by estimating freedom from the event of interest at 6 months by the Kaplan-Meier method.

Definition of time to event (days):

In case of event, time to event = [(Date of event – date of Implant visit) + 1]

In case of no event, time to event = [(Date of last available date or date of day 180 [6 months] – date of Implant visit) + 1], this data will be censored.

The event free rate and respective 95% Cis based on KM method will be compared to the null rate.

For endpoint 1:

H0: rate of freedom from device/system related complication at 6 months \leq 90 %

H1: rate of freedom from device/system related complication at 6 months $>$ 90

For endpoint 2:

H0: rate of freedom from pressure sensor failure at 6 months \leq 95 %

H1: rate of freedom from pressure sensor failure at 6 months $>$ 95 %

